7.2.2.8 Cardiac assessments

Note: As of protocol amendment 10, cardiac assessments will be performed as outlined in Table 7-2.

7.2.2.8.1 Electrocardiogram (ECG) schedule for the dual combination

At Screening/baseline a standard 12 lead ECG (local assessment) will be performed to assess eligibility. Subsequent 12-lead ECGs are to be conducted at the following time points:

- Cycle 1 Days 1 and 15 predose
- Cycle 2 Days 1 and 15 predose
- Day 1 of all subsequent cycles predose
- EOT

For all patients, prior to the first administration of the LGX818 and MEK162 combination on Cycle 1 Day 1, three sequential 12 lead ECGs, separated by at least 5-10 minutes, must be performed. The average of the triplicate ECG measurements will serve as the patient's baseline value for post-dose comparisons. Single ECGs will be performed for the other pre-dose ECGs during the study at the indicated time points, at EOT and if clinically indicated.

7.2.2.8.2 Electrocardiogram (ECG) schedule for the triple combination

At Screening/baseline a standard 12 lead ECG (local assessment) will be performed to assess eligibility. Subsequent triplicate 12-lead ECGs are to be conducted at the following time points:

- Cycle 1 Days 1 and 15: pre-dose, 1.5 hrs (± 0.5 hr) and 4 hr (± 0.5 hr) post-dose
- Cycle 2 Day 1: pre-dose, 1.5 hrs (± 0.5 hr) and 4 hr (± 0.5 hr) post-dose
- Cycle 2 Day 15: pre-dose
- Day 1 of subsequent cycles: pre-dose
- EOT

All ECGs for patients treated with the triple study drug combination should be taken before a blood sample or at least 0.5 hours after a blood sample to avoid potential effects of blood-draw on ECG readout.

For any patients who had therapy interrupted due to QTcF ≥ 481 ms, ECGs should be repeated 7 days and 14 days after dose resumption (then as clinically indicated). For all patients experiencing a grade 3 QTcF interval prolongation, hypokalemia, hypomagnesaemia and oxygenation status should be monitored.

All ECGs (except the screening ECG) for patients treated with either the dual or triple study drug combination will be independently reviewed by a central laboratory. Instructions for the collection and transmission of ECGs to the independent reviewer will be provided in the ECG Manual. Interpretation of the tracing must be made by a qualified physician and documented on the ECG eCRF page. Each ECG tracing print-out should be labeled with the study number, patient initials (where regulations permit), patient number, date, and kept in the source

documents at the study site. Clinically significant abnormalities present when the patient signed informed consent should be reported on the relevant medical history/current medical conditions eCRF page. Clinically significant findings must be discussed with the Sponsor's Medical Monitor prior to enrolling the patient in the study. New or worsened clinically significant findings occurring after informed consent must be recorded on the AE eCRF page.

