1.3.2 Triple combination LGX818 and MEK162 and LEE011

Based on the most frequent observed adverse events described for the LGX818 and MEK162 dual combination (see current LGX818 Investigator Brochure or MEK162 Investigator Brochure) and for LEE011 (see Section 1.2.3.2 and current LEE011 Investigators Brochure), overlapping toxicities can be expected for gastrointestinal events (such as nausea, vomiting, diarrhea) as well as fatigue.

Since (asymptomatic) QTc prolongation has been observed with LEE011 as a single agent, additional collection of post-dose ECGs are implemented into this trial for the triple combination. ECGs be collected in triplicate (vs. single ECGs) and the entry criteria for the triple-combination study exclude patients with congenital long QT syndrome or family history of unexpected sudden cardiac death and/or hypokalemia CTCAE Grade ≥ 3 , and patients who are currently receiving treatment with agents that are known to cause QTc prolongation in humans. During study treatment with the triple combination, use of concomitant medication known to cause QTc prolongation is prohibited.

LEE011 inhibited CYP3A4-catalyzed marker substrate reactions in vitro in human liver microsomes with Ki values of 35 μ M. Time-dependent inhibition of CYP3A4 was observed

with a K_i value of 5 μM and a K_{inact} value of 0.0245 min^{-1} . Since LGX818 is a substrate for CYP3A4, LEE011 has a potential to increase PK exposures of LGX818. *In vitro* studies indicated that LEE011 was mainly metabolized by CYP3A4. Since LGX818 is a more potent inducer than an inhibitor of CYP3A4, LGX818 may decrease the exposure of LEE011.

Quantitative assessment of potential drug-drug interaction was performed using a dynamic physiologically based PK (PBPK) model in Simcyp and the simulation confirmed the qualitative assessment. At LGX818 450 mg QD and LEE011 200 mg QD, the model predicts 29% and 14% increase in AUC and C_{max} of LGX818, respectively, as well as 47% and 30% decrease in AUC and C_{max} of LEE011, respectively.

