6.1.1.2 Administration of triple combination (LGX818 and MEK162 and LEE011)

LGX818 and LEE011 capsules will be co-administered orally once daily with MEK162 tablets twice daily. The study drugs will be administered as a flat-fixed dose, and not by body weight or body surface area.

- Patients must be instructed to take the study drug combination of one or more tablets of MEK162 and one or more capsules of LGX818 and LEE011 together with a large glass of water (~250 ml) daily in the morning at approximately the same time every day. On all dose administration days patients can take MEK162 and LGX818 and LEE011 with or without food.
- The second daily dose of MEK162 should be taken together with a glass of water irrespective of food.
- The prescribed BID doses for MEK162 should be taken 12 ± 2 hours apart.
- LEE011 will be taken for 21 consecutive days followed by a 7-day planned break (3 weeks on, 1 week off schedule). LGX818 and MEK162 are taken on a continuous schedule.

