7.2.2 Safety and tolerability assessments

Note: As of protocol amendment 10, safety assessments will be performed as indicated in [Table 7-2](#).

Safety will be monitored by assessing the procedures listed below as well as collecting of the adverse events at every visit. For details on AE collection and reporting, refer to [Section 8](#). All safety assessments should be performed pre-dose unless specified otherwise.

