10.5.2.3 Other Safety data

Any other safety information collected will be listed and notable values will be flagged. Any statistical tests performed to explore the data will be used only to highlight any interesting comparisons that may warrant further consideration. Additionally, the following outputs will be produced:

ECG

- shift table baseline to worst on-treatment result for overall assessments
- listing of ECG evaluations for all patients with at least one abnormality.

Vital signs

- shift table baseline to worst on-treatment result
- table with descriptive statistics at baseline, one or several post-baseline time points and change from baseline to this/these post-baseline time points.

Ocular

- Listing of ocular assessment for all patients with at least one abnormality will be presented.

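### From Cycle 3 on, no in-cycle ECG scheduled for the triple combination is timed to LEE011 exposure, although ECGs were added because LEE011 prolongs QTc

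*Protocol*

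**What the plan says.** - **Purpose.** Section 1.3.2 notes QTc prolongation with single-agent LEE011 and says that "additional collection of post-dose ECGs are implemented into this trial for the triple combination". It later describes post-dose and triplicate ECGs as the means of monitoring cardiac safety during triple treatment.
- **Schedule.** Section 7.2.2.8.2 starts densely: "Cycle 1 Days 1 and 15: pre-dose, 1.5 hrs (± 0.5 hr) and 4 hr (± 0.5 hr) post-dose". Cycle 2 Day 1 has the same three times. Then comes "Cycle 2 Day 15: pre-dose", then "Day 1 of subsequent cycles: pre-dose", and finally an end-of-treatment ECG.
- **Dosing.** Section 6.1.1.2: "LEE011 will be taken for 21 consecutive days followed by a 7-day planned break". LGX818 and MEK162 are continuous. Section 6.2.1 allows no delay between cycles, so study Day 29 is Day 1 of Cycle 2.
- **Now in force.** Section 7.2.2.8 hands cardiac assessments to Table 7-2 as of Amendment 10. That table has a single ECG, recommended every 8 to 12 weeks, with no cycle day. The default in section 7.2.2 is "All safety assessments should be performed pre-dose unless specified otherwise".
- **Reporting.** Section 10.5.2.3 plans a "shift table baseline to worst on-treatment result for overall assessments" for ECG and a listing of patients with abnormal ECGs.

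**The concern.** Set against the dosing calendar, the schedule looks at QTcF on LEE011 only in the first two cycles. From Cycle 3 the sole in-cycle tracing sits at the end of the planned LEE011 break. A safety measure added because of one drug is then read when that drug is largely absent.

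Two things are at stake. First, the QTcF rules in Table 6-4 act on a measured value. A change that appears on LEE011 after Cycle 2 and fades during the break need not reach them through scheduled monitoring. Section 6.2.4.2.2 lets LEE011 be raised within a patient after the fourth cycle, with no limit on the number of increases, and no scheduled ECG is timed to the new exposure. Section 1.2.3.2 reports that QTc prolongation with single-agent LEE011 became more frequent as the dose rose.

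Second, the final report will cover all Phase Ib/II triple-combination patients (section 10). A long run of normal Day 1 tracings could be read as long-term QTcF safety on the triple combination, which they cannot show for the LEE011 component.

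**Working it through.** The protocol gives no figure to reproduce. Two checks apply: a count of time points and a washout calculation.

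**1. Scheduled time points after at least one LEE011 dose in the same cycle (section 7.2.2.8.2)**

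| Cycle | Time points | Count |
|---|---|---|
| 1 | Day 1 at 1.5 h and 4 h; Day 15 pre-dose, 1.5 h, 4 h | 5 |
| 2 | Day 1 at 1.5 h and 4 h; Day 15 pre-dose | 3 |
| 3 and later | none (Day 1 pre-dose only) | 0 of 1 |

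A patient treated for 12 cycles has 10 later in-cycle ECG times (Cycles 3 to 12), all scheduled at the end of the break.

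**2. Parent LEE011 left at Day 1 pre-dose**

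Inputs: last dose on Day 21 and next Day 1 on Day 29 (sections 6.1.1.2 and 6.2.1), a gap of 8 × 24 = 192 h. Effective half-lives are 24 h at 50 mg, 31 h at 900 mg and 40 h at 600 mg (section 1.2.3.2.1).

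Formula: fraction left = 0.5^(t / half-life). Relative to the level at the last dose, t = 192 h. Relative to the steady-state trough 24 h after that dose, t = 168 h.

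| Half-life | Half-lives in 192 h | Left vs last-dose level | Left vs steady-state trough |
|---|---|---|---|
| 24 h | 8.0 | 0.4% | 0.8% |
| 31 h | 6.2 | 1.4% | 2.3% |
| 40 h | 4.8 | 3.6% | 5.4% |

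Model check: accumulation = 1 / (1 − 0.5^(24 / half-life)) gives 2.00, 2.41 and 2.94, inside the 1.55- to 2.94-fold range in section 1.2.3.2.1.

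**3. Visit window.** Section 7.1 allows ± 3 days. Three days early is Day 26, 120 h after the last dose, when 3.1%, 6.8% and 12.5% of the last-dose level is left.

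**4. Cycle 2 Day 1 post-dose.** This is a first dose after the break. With accumulation of 1.55 to 2.94, exposure is about 1/2.94 = 34% to 1/1.55 = 65% of steady state. Section 1.2.3.2.1 puts steady state by Day 8, which leaves Cycle 1 Day 15 as the only scheduled post-dose time at steady state.

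**5. Table 7-2.** Eight and twelve weeks are exactly two and three 28-day cycles, so Day 1 timing can simply continue.

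**The case against.** The strongest reply is that early, dense ECG sampling is a legitimate design. Section 1.3.2 promises additional post-dose ECGs, and they exist on three days. Cycle 1 Day 15 is at steady state. Nothing promises post-dose ECGs in later cycles, so there is no literal contradiction. That stands. The mismatch is with the stated aim of monitoring cardiac safety during triple treatment.

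A reader might infer that QTcF is never measured on LEE011 after Cycle 2. The protocol does not support this. The end-of-treatment ECG is due within 14 days of the last dose and is not tied to Day 1. A visit up to 3 days late can follow the first LEE011 doses of a cycle. After an interruption for QTcF ≥ 481 ms, ECGs are repeated 7 and 14 days after resumption. Each may fall on LEE011, but none guarantees it, and the last helps only once prolongation has been found.

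A reader might also infer that off-drug tracings dilute the ECG shift table. They do not: it takes the worst on-treatment result, which an extra normal tracing cannot lower. What it lacks is later on-drug values.

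The section 7.2.2.8.2 schedule no longer governs the 5 triple-combination patients still on treatment at Amendment 10. Table 7-2 does, and even a pre-dose ECG under it may fall within Days 2 to 21. But it is silent on cycle day, so it does not secure this.

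Two further limits stand. Day 1 tracings still inform on LGX818 and MEK162, which are dosed continuously and also covered by the Table 6-4 QTcF rules. And the single-agent rates of Grade 1 or 2 prolongation (25% at 600 and 750 mg, 31% at 900 mg, 100% at 1200 mg) cannot be carried over directly: the triple starts at 100 mg LEE011, and a 47% fall in LEE011 AUC is predicted at 200 mg with LGX818 450 mg. Table 6-2 does, however, reach 900 mg.

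**Conclusion.** The point holds in a limited form. No in-cycle ECG scheduled in section 7.2.2.8.2 from Cycle 3 on is timed to LEE011 exposure, and Table 7-2 does not close the gap. At the scheduled time, 0.8% to 5.4% of the steady-state trough remains. Late QTcF change on LEE011 can be missed by scheduled monitoring, and the later data cannot support a statement about QTcF on LEE011.

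This assumes first-order decline at the protocol's effective half-lives, no missed doses, and visits on the nominal day. It covers the parent drug only. The protocol says the metabolite LEQ803 interacts with hERG channels and probably contributes to QT effects, but gives no half-life for it. So it is not shown that all QT effect has gone by Day 1. Nor do the documents show that any late prolongation was in fact missed. The point deserves correction but does not undermine the Cycle 1 and 2 QTcF data.

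**What to change.** **Protocol.** The sponsor should reconcile the ECG timing in section 7.2.2.8.2 and Table 7-2 with the purpose in section 1.3.2 and the dosing pattern in section 6.1.1.2. The choice of timing is the sponsor's.

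**Analysis.** In section 10.5.2.3, tabulate triple-combination QTcF separately for tracings taken within a LEE011 dosing period and tracings taken after the break, classified from the dose dates already recorded on the dosage administration form. Base any statement about QTcF on LEE011 on the first group only.

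**Cost.** One extra table, no extra ECGs, and fewer tracings behind the on-LEE011 statement. For the remaining triple-combination patients the ECG visit might move within the cycle, depending on how the sponsor reconciles the sections.

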7.2.2.8.3 Cardiac imaging - MUGA (multiple gated acquisition) scan or echocardiogram

- The left ventricular heart function will be evaluated by ECHO or MUGA at Screening/baseline, during the study on Day 1 of Cycle 2, Day 1 of every third cycle until Cycle 11 (i.e. Day 1 of Cycle 5, 8 and 11) and Day 1 of every fourth Cycle thereafter (i.e. Day 1 of Cycle 15, 19 etc.), at the End of Treatment visit and if clinically indicated irrespective of the time of dosing. The same procedure should be used throughout the study.

7.2.3 Pharmacokinetics

The blood sampling regimens for determining the pharmacokinetics of MEK162 and its primary active metabolite AR00426032, LGX818, and LEE011 and its metabolite LEQ803 after oral administration of the dual or triple combination as applicable, are given in [Table 7-3](#) (dose escalation) and [Table 7-4](#) (dual-combination Phase II aims 2 and 3, and aim 1 if required as per instruction from Sponsor/ triple-combination Phase II aim A). Blood samples for LGX818, MEK162/AR00426032 and LEE011/LEQ803 (as applicable) plasma concentration measurements will be collected and evaluated on all patients enrolled in the dose escalation and on a selected number of patients in the dual-combination Phase II aims 2 and 3 (and aim 1 if required as per instruction from the Sponsor for assessment of the potential impact of demographic differences (e.g. Japanese vs Caucasian) and triple-combination Phase II aim A, parts of the study.

In addition to LGX818, MEK162/AR00426032 and LEE011/LEQ803 analyses, **CCI**

Plasma samples remaining from the analysis may be retained by the Sponsor for additional investigations (e.g. long term stability, reproducibility).

A detailed description of the planned pharmacokinetic analyses is given in [Section 10.5.3](#).

7.2.3.1 Pharmacokinetic blood sample collection and handling

7.2.3.1.1 Blood collection plan

Dose Escalation: From all patients treated in the dose escalation part, blood for full pharmacokinetic profiling of LGX818 and MEK162, and LEE011 if applicable will be collected on Cycle 1 Days 1 and 15 (including a 24 hr post dose sample on the following day; see [Table 7-4](#)). Additionally, pre-dose samples will be collected on Day 1 of Cycle 2 through Cycle 10.

Dual combination Phase II arm 1: No PK sampling will be performed for patients enrolled in this arm. The exception to this is for newly enrolled patients in which an assessment of the potential impact of demographic differences on the PK of the LGX818 and MEK162 combination may be made, if required as per instruction from the Sponsor.

Dual combination Phase II arms 2 and 3: From the first 10 patients in each arm, and if required as per instruction from the Sponsor, from additional patients in which an assessment of the potential impact of demographic differences on the PK of the LGX818 and MEK162 combination may be made. Blood for pharmacokinetic profiling of LGX818 and MEK162 will be collected on Cycle 1 Days 1 and 15 (including a 24 hr post dose sample on the following day; see Table 7-4) to study the CCI of the study drug dual combination. The 4- and 6-hour post-dose samples collected during dose escalation are replaced with a 5-hour post-dose sample for these patients to collect less blood from the patients but still cover the PK profile of the study drugs. Additionally, pre-dose samples will be collected on Day 1 of Cycle 2 through Cycle 10 for those patients.

PK blood sample collection time points will remain the same if the dosing schedule of LGX818 would change to a BID and/or QOD dosing schedule.

Triple-combination Phase II arm A: From the first 10 patients, blood for pharmacokinetic profiling of LGX818 and MEK162 and LEE011 will be collected on Cycle 1 Days 1 and 15 (including a 24 hr post dose sample on the following day; see Table 7-4) to study the CCI of the study drug triple combination. Additionally, pre-dose samples will be collected on Day 1 of Cycle 2 through Cycle 10 for those patients.

For all patients from whom PK samples are collected (either treated with the dual or triple combination), exact dates and clock times of drug administration and actual PK blood draw will be recorded on the appropriate eCRF. Any sampling problems (e.g. patient took study drug before draw took place) must be noted in the comments section of the eCRF and on appropriate source documentation. The time of the last meal should be recorded on PK sampling days Cycle 1 Days 1 and 15 on the appropriate eCRF.

If vomiting or diarrhea occurs within 4 hrs following study drugs administration on the days of full PK blood sampling, the exact time (using the 24-h clock) of any vomiting or diarrhea episode should be recorded in a separate section of the eCRF in addition to recording this on the AE eCRF.

Complete instructions for sample collection, processing, handling and shipment will be provided in the [CMEK162X2110 Laboratory Manual].

Table 7-4 Schedule of blood sample collections for PK in dose escalation

Cycle	Day	PK collection No. LGX818	PK Sample No. LGX818	PK collection No. MEK162	PK sample No. MEK162	PK collection No. LEE011 ^a	PK sample No. LEE011 ^a	Scheduled time relative to dosing
1	1	101	101	201	201	501	501	Pre-dose*
1	1	101	102	201	202	501	502	0.5 hr post dose
1	1	101	103	201	203	501	503	1.5 hr post dose
1	1	101	104	201	204	501	504	2.5 hr post dose
1	1	101	105	201	205	501	505	4 hr post dose

Cycle	Day	PK collection No. LGX818	PK Sample No LGX818	PK collection No. MEK162	PK sample No. MEK162	PK collection No. LEE011 ^a	PK sample No. LEE011 ^a	Scheduled time relative to dosing
1	1	101	106	201	206	501	506	6 hr post dose
1	1	101	107	201	207	501	507	8 hr post dose
1	2	102	108	202	208	502	508	24 hr post dose immediately prior to dosing on C1D2
1	15	103	109	203	209	503	509	Pre-dose*
1	15	103	110	203	210	503	510	0.5 hr post dose
1	15	103	111	203	211	503	511	1.5 hr post dose
1	15	103	112	203	212	503	512	2.5 hr post dose
1	15	103	113	203	213	503	513	4 hr post dose
1	15	103	114	203	214	503	514	6 hr post dose
1	15	103	115	203	215	503	515	8 hr post dose
1	16	104	116	204	216	504	516	24 hr post dose immediately prior to dosing on C1D16**
2	1	105	117	205	217	505	517	Pre-dose*
3	1	106	118	206	218	506	518	Pre-dose*
4	1	107	119	207	219	507	519	Pre-dose*
5	1	108	120	208	220	508	520	Pre-dose*
6	1	109	121	209	221	509	521	Pre-dose*
7	1	110	122	210	222	510	522	Pre-dose*
8	1	111	123	211	223	511	523	Pre-dose*
9	1	112	124	212	224	512	524	Pre-dose*
10***	1	113	125	213	225	513	525	Pre-dose*
NA	NA	NA	1001+	NA	2001+	NA	5001+	Unscheduled****

*Collect PK sample immediately prior to the start of oral study drug combination (LGX818 and MEK162 or LGX818 and MEK162 and LEE011) administration.
 **Schedule PK collection together with collection fresh tumor and skin biopsy (if applicable). If it is not possible to collect the tumor and skin biopsy on C1D16, then an additional unscheduled pre-dose PK sample should be collected on the day fresh tumor biopsy and skin biopsy is collected. For patients for who a fresh skin/tumor biopsy is not collected, the C1D16 PK sample should be collected on the scheduled time point and day. The PK sample at this time point should be collected prior to the collection of the blood for genetic analysis sample.
 *** Pre-dose PK samples will be collected up to Cycle 10 only.
 ****Applies only to samples collected before effective date of Protocol Amendment Version 09. Unscheduled PK samples will be uniquely, sequentially numbered 1001, 1002 etc. for LGX818 and 2001, 2002 etc for MEK162 and 5001, 5002 etc for LEE011.
^a only for patients treated with the triple study drug combination.

Table 7-5 Schedule of blood sample collections for PK in dual-combination Phase II arms 2 and 3, (and arm 1 if required^a) / triple-combination Phase II arm A

Cycle	Day	PK collection No. LGX818	PK Sample No LGX818	PK collection No. MEK162	PK sample No. MEK162	PK collection No. LEE011 ^b	PK sample No. LEE011 ^b	Scheduled time relative to dosing
1	1	301	301	401	401	601	601	Pre-dose*
1	1	301	302	401	402	601	602	0.5 hr post-dose

Cycle	Day	PK collection No. LGX818	PK Sample No LGX818	PK collection No. MEK162	PK sample No. MEK162	PK collection No. LEE011 ^b	PK sample No. LEE011 ^b	Scheduled time relative to dosing
1	1	301	303	401	403	601	603	1.5 hr post dose
1	1	301	304	401	404	601	604	2.5 hr post dose
1	1	301	305	401	405	601	605	5 hr post dose
1	1	301	306	401	406	601	606	8 hr post dose
1	2	302	307	402	407	602	607	24 hr post dose immediately prior to dosing on C1D2
1	15	303	308	403	408	603	608	Pre-dose*
1	15	303	309	403	409	603	609	0.5 hr post-dose
1	15	303	310	403	410	603	610	1.5 hr post dose
1	15	303	311	403	411	603	611	2.5 hr post dose
1	15	303	312	403	412	603	612	5 hr post dose
1	15	303	313	403	413	603	613	8 hr post dose
1	16	304	314	404	414	604	614	24 hr post dose immediately prior to dosing on C1D16**
2	1	305	315	405	415	605	615	Pre-dose*
3	1	306	316	406	416	606	616	Pre-dose*
4	1	307	317	407	417	607	617	Pre-dose*
5	1	308	318	408	418	608	618	Pre-dose*
6	1	309	319	409	419	609	619	Pre-dose*
7	1	310	320	410	420	610	620	Pre-dose*
8	1	311	321	411	421	611	621	Pre-dose*
9	1	312	322	412	422	612	622	Pre-dose*
10***	1	313	323	413	423	613	623	Pre-dose*
NA	NA	NA	3001+	NA	4001+	NA	6001+	Unscheduled****

^a Only for newly enrolled patients in which an assessment of the potential impact of demographic differences on the PK of the LGX818 and MEK162 combination may be made, if this assessment is required.

^b Only for patients treated with the triple study drug combination.

*Collect PK sample immediately prior to the start of oral study drug combination (LGX818 and MEK162 or LGX818 and MEK162 and LEE011) administration.

**Schedule PK collection together with collection fresh tumor and skin biopsy. If it is not possible to collect the tumor and skin biopsy on C1D16, then an additional unscheduled pre-dose PK sample should be collected on the day fresh tumor biopsy and skin biopsy is collected. The PK sample at this time point should be collected prior to the collection of the blood for genetic analysis sample.

*** Pre-dose PK samples will be collected up to Cycle 10 only.

**** Applies only to samples collected before effective date of Protocol Amendment Version 09. Unscheduled PK samples will be uniquely, sequentially numbered 3001, 3002 etc. for LGX818 and 4001, 4002 etc for MEK162 and 6001, 6002 etc for LEE011.

